### ***Effect of biomarkers on the primary endpoint***

The effect of the biomarkers at baseline and high resolution HLA (class I) genotyping on the primary endpoint will be explored one variable at a time.

For continuous variables, the analysis will be made by adding the biomarker at baseline (log-transformed) as a fixed effect covariate with a coefficient that depends on visit and treatment to the MMRM described for the primary endpoint. The estimated effect of the variable at selected time points including week 54 will be presented with a 95% CI for each treatment.

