#### Secondary objectives

Objectives related to treatment period (from baseline (week 0) to week 54):

- To assess safety and tolerability of NNC0114-0006 and liraglutide in combination and alone in subjects with newly diagnosed T1DM
- To assess effect on glycaemic parameters (including insulin usage and insulin regimen) of NNC0114-0006 and liraglutide in combination and alone in subjects with newly diagnosed T1DM
- To assess pharmacokinetic (PK) properties of NNC0114-0006 and liraglutide in combination and alone in subjects with newly diagnosed T1DM
- To explore biomarkers relevant for the effect of NNC0114-0006 and liraglutide in combination and alone in subjects with newly diagnosed T1DM
- To assess disease burden and health status in subjects with newly diagnosed T1DM treated with NNC0114-0006 and liraglutide in combination and alone

Objectives related to the post-treatment observation period (from week 54 to week 80):

- To assess post-treatment safety and tolerability of NNC0114-0006 and liraglutide in combination and alone in subjects with newly diagnosed T1DM
- To assess post-treatment effect on preservation of beta-cell function of NNC0114-0006 and liraglutide in combination and alone in subjects with newly diagnosed T1DM
- To assess post-treatment effect on glycaemic parameters (including insulin usage and insulin regimen) of NNC0114-0006 and liraglutide in combination and alone in subjects with newly diagnosed T1DM
- To explore biomarkers relevant for the post-treatment effect of NNC0114-0006 and liraglutide in combination and alone in subjects with newly diagnosed T1DM

- To assess post-treatment development of disease burden and health status in subjects with newly diagnosed T1DM treated with NNC0114-0006 and liraglutide in combination and alone

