## 2 Statistical considerations

Based on the statistical model, treatment means or geometric means (LSMeans) and treatment comparisons (i.e. treatment differences or treatment ratios) will be presented with 95% confidence intervals (CI) and p-values for the two-sided test of no treatment difference. A significance level of

5% will be used. All pairwise treatment differences (or ratios) will be presented. No adjustment for multiple testing will be performed.

Some endpoints will be summarised for the treatment period, for the observation period and for the entire trial period (i.e. the treatment period together with the observation period)

The treatment period and the observation period will be derived for completed subjects as

- The start of the treatment period will be the date of first trial product administration
- The end of the treatment period will be the date of the visit at week 54 (i.e. the day of visit 63)
- The start of the observation period will be the day after the end of the treatment period
- The end of the observation period will be the date of the last visit

For withdrawn subjects the date of last contact will be the maximum of the date of the last visit and the withdrawal date. The treatment period and the observation period will be derived for withdrawn subjects as

- The start of the treatment period will be defined as described for completed subjects
- The end of the treatment period will be as defined for completed subjects if this date is before or on the date of last contact. Otherwise the end of the treatment period will be the date of last contact
- An observation period will only be defined if the date of last contact is after the end of the treatment period
  - The start of the observation period will be defined as for completed subjects
  - The end of the observation period will be the date of last contact

For endpoints evaluated as change from baseline and/or for baseline adjustment in the statistical analyses, baseline will be defined as the information recorded at the Visit 3 (randomisation). If no measurement is available at Visit 3, then the information recorded at Visit 2 will be used as the baseline. Furthermore, if no measurement is available at Visit 2, then the information recorded at Visit 1 will be used as the baseline.

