## 2.1 Sample size calculation

This is a phase 2 trial and the first Novo Nordisk trial of NNC0114-0006 in subjects with newly diagnosed T1DM. Therefore the knowledge on treatment effects and on the standard deviation of the primary endpoint is limited.

The statistical power calculations have been done under the following assumptions

- The primary endpoint is  $AUC_{0-4h}$  for a MMTT stimulated C-peptide concentration-time curve at week 54 relative to baseline, i.e.  $AUC_{0-4h, C-peptide, 54w} / AUC_{0-4h, C-peptide, baseline}$ . The primary endpoint will be log-transformed in the statistical analysis and this will be denoted  $\ln(AUC_{0-4h, C-peptide, \Delta 54w})$ . Thus,  $AUC_{0-4h, C-peptide, \Delta 54w}$  is the proportion of  $AUC_{C-peptide}$  that is preserved after 54 weeks relative to the level at baseline. E.g. a reduction of  $AUC_{C-peptide}$  of 35% corresponds to a preservation of 65% and value of the  $\ln(AUC_{0-4h, C-peptide, \Delta 54w})$  is  $\ln(0.65) = -0.431$ .
- The residual standard deviation of  $\ln(AUC_{0-4h, C-peptide, \Delta 54w})$  in the model described above may depend on the treatment. Based on the results of Herold et al. the standard deviation is assumed to be 1 in the placebo group and 0.5 in the group treated with NNC0114-0006 in combination with liraglutide.
- The expected preservation in the placebo treated patients is 65%, based on the results of Herold et al. who found a mean of 70% decline in  $AUC_{C-peptide}$  over a 24-months period. Assuming a linear decline, the mean 12-months decline would be 35%, i.e. a preservation of 65%. The statistical power calculations have been done assuming three levels of treatment effects for NNC0114-0006 in combination with liraglutide; a preservation of 85% and 95% and 98%, respectively.

[Table 2-1](#) shows the statistical power for the test of no treatment effect if the true mean preservation is 85%, 95% or 98% in the group treated with NNC0114-0006 in combination with liraglutide and 65% in the placebo group when the numbers of completers are 40, 60 or 80, respectively using a two-sided test and 5% level of significance. The rows corresponding to the chosen number of (completing) subjects are highlighted.

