## **Exploratory analyses**

### ***Effect of stratum on the primary endpoint***

An exploratory analysis will be made to investigate a potential interaction between treatment and stratum for the primary endpoint. The analysis will be made by adding the interaction between stratum, treatment and visit as a factor in the mixed model for repeated measurements (MMRM) described for the primary endpoint. The treatment means and the treatment ratios at selected time points including week 54 will be presented with 95% CIs for each stratum separately.

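### The stratum and biomarker analyses in SAP 2.3 fit treatment-dependent terms but plan no contrast that measures effect modification

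*SAP*

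**What the plan says.** Under *Effect of stratum on the primary endpoint* (SAP 2.3, Exploratory analyses) the aim is explicit: "An exploratory analysis will be made to investigate a potential interaction between treatment and stratum for the primary endpoint". A stratum-by-treatment-by-visit term is added to the primary MMRM. The planned output is: "The treatment means and the treatment ratios at selected time points including week 54 will be presented with 95% CIs for each stratum separately".

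Under *Effect of biomarkers on the primary endpoint*, each continuous baseline biomarker enters the same model, log-transformed, with a coefficient that varies by visit and by treatment. The planned output is: "The estimated effect of the variable at selected time points including week 54 will be presented with a 95% CI for each treatment".

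The general reporting rule in SAP Section 2 calls for estimates, intervals and "p-values for the two-sided test of no treatment difference", for all pairwise treatment comparisons and without multiplicity adjustment. It concerns treatment differences or ratios. It does not mention differences between slopes or comparisons of treatment ratios across strata.

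One secondary objective (SAP 1.1.1) is: "To explore biomarkers relevant for the effect of NNC0114-0006 and liraglutide in combination and alone in subjects with newly diagnosed T1DM". Protocol 5.2 gives as a reason for stratifying that the effect of NNC0114-0006 may depend on residual beta-cell function.

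**The concern.** If the question is whether the treatment effect depends on a stratum or a biomarker, the null hypothesis is one of equality: equal treatment ratios in the two strata, or equal slopes in the arms. Both models contain the term that addresses this. The planned output addresses something else, namely whether each stratum's ratio differs from 1 and whether each arm's slope differs from 0.

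A reader given only those results will tend to note that one interval excludes the null and another does not, and to take the disagreement as effect modification. That comparison does not test equality. Two estimates of the same true quantity often fall on opposite sides of the significance line.

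The results have a use. SAP 2.4.2 says that the sponsor unblinds after visit 63 for an internal analysis to inform future trials, and SAP 2.2 allows biomarker data to be examined after that lock. A contrast not specified now would be chosen after the code break.

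**Working it through.** **Inputs.** SAP 2.1 plans "using a two-sided test and 5% level of significance", with the SD of the log endpoint "assumed to be 1 in the placebo group and 0.5 in the group treated with NNC0114-0006" plus liraglutide. Preservation is 65% on placebo and 85%, 95% or 98% on the combination. Protocol 6.1 expects 240 completers, so 240/4 = 60 per arm. The documents do not give stratum sizes (Protocol 5.2 sets no cap), so I take splits from 50:50 to 20:80 as an assumption. They do not give a biomarker's prognostic strength either, so I take a common slope of 0 to 0.5 on the log endpoint per SD of log biomarker.

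**The plan's own figure.** Effect = ln(0.98/0.65) = 0.411. SE = sqrt(1/60 + 0.25/60) = 0.144. Ratio = 2.845. Power is 0.812 by the normal approximation and 0.803 with Satterthwaite degrees of freedom, against 0.804 in SAP Table 2–1. With Satterthwaite degrees of freedom all nine cells reproduce to about 0.001.

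**Stratum analysis, same true effect in both strata.** In a stratum with n per arm, SE = sqrt(1.25/n). If the powers are p1 and p2, the chance that exactly one interval excludes 1 is p1(1−p2) + p2(1−p1). With Satterthwaite t:

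| True preservation, combination | Split | Power, larger stratum | Power, smaller stratum | Exactly one excludes 1 |
|---|---|---|---|---|
| 98% | 50:50 | 0.502 | 0.502 | 0.500 |
| 98% | 30:70 | 0.649 | 0.322 | 0.553 |
| 98% | 20:80 | 0.708 | 0.224 | 0.615 |
| 95% | 50:50 | 0.443 | 0.443 | 0.494 |
| 95% | 20:80 | 0.640 | 0.198 | 0.585 |
| 85% | 50:50 | 0.250 | 0.250 | 0.375 |
| 85% | 20:80 | 0.374 | 0.123 | 0.405 |
| 65% (no effect) | any | 0.050 | 0.050 | 0.095 |

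The normal approximation gives 0.499 and 0.612 at 98%, and 0.385 and 0.414 at 85%. Simulation at 50:50 (4,000 runs) gives 0.507, 0.386 and 0.102 for 98%, 85% and no effect.

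**Biomarker analysis, same true slope in combination and placebo.** Slope SE = SD/sqrt(60). The table gives the chance that one arm's interval excludes 0 and the other's does not. The common SD is sqrt((1 + 0.25)/2) = 0.79.

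| Common slope | SDs 1 and 0.5 | Common SD 0.79 |
|---|---|---|
| 0 | 0.095 | 0.095 |
| 0.1 | 0.379 | 0.276 |
| 0.2 | 0.619 | 0.500 |
| 0.3 | 0.359 | 0.274 |
| 0.4 | 0.127 | 0.049 |
| 0.5 | 0.028 | 0.003 |

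For two equally powered arms the rate is 2p(1−p), which peaks at 50% when p = 0.5.

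**Direct contrast, same scenarios, 4,000 runs each.** The ratio of treatment ratios (50:50 split, SDs 1 and 0.5) is falsely significant in 5.0% to 5.5% of trials. The slope difference (common SD 0.79, slopes 0 to 0.3) is falsely significant in 4.3% to 5.3%.

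**Precision of the stratum contrast.** At 50:50, SE = sqrt(1.25/30 + 1.25/30) = 0.289, so the 95% interval spans a factor of exp(1.96 × 0.289) = 1.76 either way. At 20:80, SE = sqrt(1.25/12 + 1.25/48) = 0.361, a factor of 2.03.

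These calculations use week-54 completers and ignore covariate adjustment and earlier visits in the MMRM.

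**The case against.** Four points can be made for the plan.

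- **The stratum analysis does report between-arm contrasts.** A treatment ratio within a stratum is one. A reader might infer that neither analysis compares arms, and the SAP's output sentence for the stratum analysis contradicts that. Only the comparison of those ratios across strata is absent. This point stands.
- **The biomarker text does not name effect modification.** Its stated subject is the effect of biomarkers on the primary endpoint, and the secondary objective can be read as served by the biomarker change endpoints in SAP 2.4.1.1, which do have treatment differences. This stands as a reading. Still, a slope that varies by treatment has little purpose other than comparing slopes.
- **The error rates assume a rule the SAP never states**, that modification is declared when one interval excludes the null and another does not. This stands, so the rates describe a natural misreading and are not a property of the plan. The SAP offers no other basis for a conclusion.
- **Both analyses are exploratory.** No subgroup claim or enrichment rule depends on them, a reader could approximate the contrast from the reported intervals, and SAP Section 2 permits supplementary analyses. This lowers the weight of the point. It is no reason to leave out an estimate that the fitted model already supplies.

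**Conclusion.** The gap is real and modest. The stratum analysis names an interaction as its aim and plans no estimate of it. The biomarker analysis models slopes by arm and plans no comparison of them. The general reporting rule fills neither gap.

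If intervals are compared by significance, a uniform effect at the SAP's design values looks different between strata in about 50% to 61% of trials. At 85% preservation the figure is 38% to 41%, and with no effect it is 9.5%. These rest on the SAP's effects and SDs and on assumed stratum splits. For biomarkers the rate is roughly 5% to 60% over common slopes of 0 to 0.4, and lower at 0.5. A direct contrast errs about 5% of the time, per contrast.

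Two stronger conclusions are tempting. One is that false modification will appear about half the time in general. That holds only near the design effect for strata, and for biomarkers only at particular assumed strengths. The other is that a false responder subgroup will be carried into later trials. The documents attach no decision to these analyses, so that remains a possibility only. The primary analysis is unaffected.

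**What to change.** In SAP 2.3, add to the two exploratory analyses, from the models already specified:

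- **Stratum:** the week-54 ratio of treatment ratios, >0.6 over 0.2–0.6 nmol/l, for each active arm versus placebo, with 95% CI.
- **Biomarkers:** the week-54 difference in slope of each active arm versus placebo, with 95% CI, for each continuous biomarker.

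Label both exploratory. State that any p-values are unadjusted for multiplicity. With three contrasts per variable and many biomarkers, the chance of at least one false positive exceeds 5%. State also that effect modification is assessed from these contrasts, and keep the arm-specific and stratum-specific estimates as descriptive output.

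The cost is a few lines of SAP text and estimate statements for each model. No new data are needed and the primary analysis does not change. The contrasts will be imprecise, as the interval widths above show, and the report should say so.

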### ***Effect of liraglutide concentration on the primary endpoint***

An exploratory analysis will be made to investigate a potential effect of the concentration of liraglutide on the primary endpoint using data from the two groups of subjects treated with liraglutide. This analysis will be made by adding the log-transformed concentration of liraglutide measured on the date corresponding to the last MMTT as a covariate in the analysis using LOCF for the primary endpoint.

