#### 5.3.2 Liraglutide

Liraglutide and liraglutide placebo will be self-administered s.c. either in the abdomen, thigh or upper arm daily with a pen-injector around the same time of the day, when the most convenient time of the day has been chosen. The last dose of liraglutide will be administered at the day prior to the Visit 63 (week 54).

Liraglutide and insulin should not be injected in close physical proximity.

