# 6 Trial population

# 6.1 Number of subjects

Number of subjects planned to be screened: 600

Number of subjects planned to be randomised: 304

Maximum number of subjects to be randomised: 314

Number of subjects expected to complete the trial (defined as reaching primary endpoint): 240

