#### 8.1.7 Withdrawn subjects

If a subject is withdrawn from the trial during the treatment period (week 0-54), the investigator must aim to undertake procedures similar to those for Visit 63 as soon as possible and perform the safety follow up visit (Visit 90)  $15 \pm 1$  weeks after last dose of NNC0114-0006. Subjects will be instructed to use appropriate pregnancy prevention until 15 weeks after last dose of NNC0114-0006. The end-of-trial form must be completed, and final drug accountability must be performed even if the subject is not able to come to the trial site. A withdrawal session must be made in the IV/WRS. The case book must be signed after all queries have been closed.

If a subject is withdrawn from the trial during the observation period (week 55-80), the investigator must aim to undertake procedures similar to those for Visit 89 as soon as possible and the safety follow up visit (Visit 90)  $15 \pm 1$  weeks after last dose of NNC0114-0006. Subjects withdrawn 14 weeks or more after last dose of NNC0114-0006 should not attend Visit 90. The end-of-trial form must be completed. A withdrawal session must be made in the IV/WRS. The case book must be signed after all queries have been closed.

Additional follow-up of subjects due to adverse events (AEs) or pregnancy is described in Section 12.3 and 12.5.

If subjects fails to return for these visits or is unable to do so, every effort should be made by the investigator to contact him/her by phone or by sending appropriate correspondence (i.e., certified letter) that will become part of the investigators' file to record that efforts were made to reach the subject.

Although a subject is not obliged to give his/her reason(s) for withdrawing from a trial, the investigator must make a reasonable effort to ascertain the reason(s), while fully respecting the subject's rights. Where the reasons are obtained, the primary reason for not completing the trial must be specified on the end-of-trial form in the eCRF.

If new information becomes available which the safety committee at Novo Nordisk concludes would compromise the safety of the subjects, the trial will be permanently discontinued. In such cases, the subjects will still need follow-up visits as described above, i.e. at discontinuation and at 15 weeks  $\pm 1$  week after last dosage of NNC0114-0006 dosage for safety reasons.

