#### Instructions prior to MMTT visits

The subject should be instructed to:

- Follow normal routine on the days prior to the MMTT visit regarding eating however the subject should attend the MMTT visit fasting
- Follow normal exercise and refrain from hard exercise (comparable to and exceeding 5 km running or weightlifting) 24 hours prior to the MMTT
- Minimise physical activity in the morning of the MMTT to the extent possible
- Refrain from intake of alcohol and use of medications that affect motility (i.e. prokinetics, anticholinergic, tricyclic antidepressants) 24 hours prior to the MMTT
- Not to take their basal insulin after 22.00 the evening before the MMTT visit
- Subjects who normally take basal insulin in the morning should bring their basal insulin to the MMTT
- Not to take any bolus insulin later than 2 hours prior to the MMTT
- Remember to bring their bolus insulin to the MMTT visits (to be given after MMTT)
- Take liraglutide/liraglutide placebo at the same time as usual both the day before the MMTT visit and on the day of the MMTT
- Remember to bring their liraglutide/liraglutide placebo to the MMTT visits, if applicable
- Remember to bring their BG meter provided for this trial
- Remember the importance of having BG on target

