### 2.3 Primary endpoint

The primary endpoint is  $AUC_{0-4h}$  for a MMTT stimulated C-peptide concentration-time curve at week 54 relative to baseline:  $AUC_{0-4h, C-peptide, 54w} / AUC_{0-4h, C-peptide, baseline}$ .

The  $AUC_{0-4h}$  for MMTT stimulated C-peptide is derived at baseline and at 12, 24, 36, and 54 weeks and is denoted  $AUC_{0-4h, C-peptide, t}$ , where  $t$  is the time of the assessment. Thus,  $t=54$  weeks corresponds to the primary endpoint.

More specifically,  $AUC_{0-4h, C-peptide, t}$  at time 't' will be determined as the area from 0 to 4 hours under the C-peptide concentration profile after a MMTT using the trapezoidal method based on observed concentration values and actual measurement times. If the MMTT is stopped before 4 hours due to hyperglycaemia or hypoglycaemia, the last measured C-peptide concentration will be carried forward for calculation of the primary endpoint. If the MMTT is stopped before 4 hours it will most likely be due to hyperglycaemia as hypoglycaemia is not expected when a high amount of carbohydrates are ingested. Using last observation carried forward (LOCF) will result in an overestimated AUC since the C-peptide response is expected to be at the maximum level during hyperglycaemia. Furthermore, the risk of hyperglycaemia during MMTT will be higher in the placebo group if the active treatments have an effect on beta-cell preservation. Thus, LOCF is considered as a conservative approach. In case the MMTT is stopped before 4 hours for reasons that are not due to hyperglycaemia or hypoglycaemia, the remaining C-peptide concentrations will be set to  $lloq/2$ .

Let  $y_{it}$  denote the value of  $AUC_{0-4h, C-peptide, \Delta t}$  evaluated relative to baseline at time  $t$  for subject  $i$ , i.e.

$$y_{it} = \text{AUC}_{0-4h, \text{ C-peptide}, \Delta t} = \text{AUC}_{0-4h, \text{ C-peptide}, t} / \text{AUC}_{0-4h, \text{ C-peptide}, \text{ baseline}}$$

log of  $y_{it}$  will be analysed using an (MMRM) including all available assessments over time with treatment, stratum and sex as factors and  $\ln(\text{AUC}_{0-4h, \text{ C-peptide}, \text{ baseline}})$  and age at baseline as covariates (see [Table 2-2](#)). The interaction between all variables and visit (week) will be included in the model as fixed effects.

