### Sensitivity analyses of the primary endpoint

The following sensitivity analyses will be made

- To assess the impact of the endpoints calculated from MMTT that is stopped before 4 hours due to hyperglycaemia or hypoglycaemia, a sensitivity analysis will be performed excluding these endpoints.

- To assess the impact of the endpoints calculated from MMTT profile that includes imputed values, a sensitivity analysis will be performed excluding these endpoints.
- A sensitivity analysis will be performed excluding endpoints calculated from the MMTT, where the date of the MMTT is more than one day after the last liraglutide dosing.
- An analysis using last observation carried forward (LOCF) of the primary endpoint. The analysis will be made using a normal linear regression model for the log-transformed primary endpoint with treatment, stratum and sex as fixed factors and age and baseline value (log-transformed) as covariates.
- An analysis based on the subjects completing the treatment period (i.e. completing the visit at week 54). The analysis will be made using a normal linear regression model for the log-transformed primary endpoint with treatment, stratum and sex as fixed factors and age and baseline value (log-transformed) as covariates
- In case the assumption of equal variance-covariance between the treatments turns out not to be reasonable a sensitivity analysis will be added where the variance-covariance matrix for the repeated measurements for each subject will depend on treatment.

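### The exploratory liraglutide concentration analysis takes outcome and concentration from the same last MMTT without allowing for when that test took place, so time of dropout can confound the coefficient

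*SAP*

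**What the plan says.** SAP 2.3, under the effect of liraglutide concentration on the primary endpoint, uses only the two liraglutide arms and works by "adding the log-transformed concentration of liraglutide measured on the date corresponding to the last MMTT as a covariate in the analysis using LOCF". The base analysis is listed among the sensitivity analyses as "An analysis using last observation carried forward (LOCF) of the primary endpoint", and it is fitted with the following model: "normal linear regression model for the log-transformed primary endpoint with treatment, stratum and sex as fixed factors and age and baseline value". The baseline enters on the log scale. Visit, or time of the last test, is not among its terms.

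The C-peptide AUC "is derived at baseline and at 12, 24, 36, and 54 weeks", so a carried-forward value may come from week 12, 24 or 36. It may also come from a withdrawal visit. Protocol 8.1.7 says that for a subject withdrawn during treatment "the investigator must aim to undertake procedures similar to those for Visit 63 as soon as possible", and Visit 63 includes both an MMTT and a liraglutide sample. The SAP does not say whether such a test counts as the last one. Read plainly, it does.

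On dosing around the tests, Protocol 8.3.1 tells subjects: "Take liraglutide/liraglutide placebo at the same time as usual both the day before the MMTT visit and on the day of the MMTT". Protocol Amendment 2 rewords this without changing its substance. Protocol 5.3.2 puts the last liraglutide dose on the day before Visit 63.

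The SAP does foresee MMTTs done off liraglutide. One sensitivity analysis of the primary endpoint drops tests taken more than one day after the last dose. That exclusion is not applied to the concentration analysis.

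**The concern.** The stated question is whether concentration affects the week-54 endpoint. The planned regression relates a ratio measured at a varying time to a concentration measured at that same varying time. Two things must hold for this to mislead.

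- The ratio falls with time, so an early last test carries a higher ratio.
- Concentration differs systematically between early and week-54 last tests.

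If both hold, the coefficient partly measures who left early. Early tests with higher concentrations push it towards an apparent benefit of concentration; early tests off drug push it towards an apparent harm. What is at stake is the reading of an exploratory coefficient, not the primary comparison.

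**Working it through.** **Plan's own figure.** The documents give no figure for this analysis, so I checked the planning inputs on the power table. For 98% against 65% preservation, SD 0.5 against 1 and 60 completers per arm:

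- difference ln(0.98/0.65) = 0.411
- SE = √((1 + 0.25)/60) = 0.144
- unequal-variance t-test power = 80.3%, against the stated 80.4%.

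**Inputs from the documents.**

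- 304 randomised 1:1:1:1, so 152 in the two liraglutide arms.
- "Number of subjects expected to complete the trial (defined as reaching primary endpoint): 240". Hence 304 − 240 = 64 non-completers, 64/304 = 21%, about 32 of them in these arms. This is an upper bound for early last tests, because a subject who leaves before week 12 without a withdrawal MMTT has nothing to carry forward.
- Planning pairs (SAP 2.1): 65% preservation with SD 1 (placebo); 85%, 95% or 98% with SD 0.5 (combination). No value is given for liraglutide alone.

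**Assumptions, not in the documents.** Log ratio linear in time; early last tests equally at weeks 12, 24 and 36 (mean 24); within-visit SD of log concentration 0.5; shift d in log concentration for early tests. I take d = 0, +0.3 and +0.7 for tests on drug and −3 for tests off drug.

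**Spurious slope with no true effect.** At 65% preservation the early-test excess in log ratio is g = 0.431 × (54 − 24)/54 = 0.239. With p = 0.21, p(1 − p) = 0.166, and

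slope = p(1 − p)·d·g / (0.25 + p(1 − p)·d²).

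- d = +0.7: 0.166 × 0.7 × 0.239 / 0.331 = +0.084
- d = −3: −0.166 × 3 × 0.239 / 1.746 = −0.068
- d = 0: zero

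For d = −3 and SD 1, the SE is 1/√(152 × 1.746) = 0.061. The mean z is then −1.1, and about 20% of tests reject. Simulation of the planned regression gives the same slopes.

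**Simulated two-sided rejection, true effect zero, 21% early last tests.**

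| Preservation, SD | no shift | +0.3 | +0.7 | half of early tests off drug | all off drug |
|---|---|---|---|---|---|
| 65%, SD 1 | 5% | 6% | 9% | 11% | 17–19% |
| 85%, SD 0.5 | 5% | 6% | 8% | 8% | about 12% |
| 98%, SD 0.5 | 5% | 5% | 5% | 5% | 5% |
| 65%, SD 0.5 | 5% | 9% | 20% | 27% | 50–59% |

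The ranges in the last column reflect timing: the lower end spreads withdrawal tests over weeks 1–54, and the upper end puts them at weeks 12, 24 and 36. With 5% early tests instead of 21%, at 65% preservation, shifts up to +0.7 give 5–7%, and all early tests off drug gives 8% (SD 1) or 18% (SD 0.5).

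**After the change.** Adding time of the last MMTT to the regression brings rejection to 4.3–5.7% when the SD is constant over time (3.0–5.7% if it grows with time). Using only observed week-54 tests gives about 5%.

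**The case against.** The strongest reply is that taking both variables from one test does not make time drive concentration. Protocol 5.3.2 escalates in two-week steps, so the target dose is planned for week 4 and then held; the first on-treatment MMTT is at week 12. With no concentration shift the test keeps its level. This stands, and it is why the point is conditional.

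A reader might set the instruction to dose on test days against the last dose on the day before Visit 63, and infer a large on-drug gap between early and week-54 samples. The documents do not support a size for it. Protocol 8.1.8 has trial product withheld at fasting visits until blood is drawn. Protocol 8.5.2.2 requires antibody samples before trial product, and Visits 19, 31, 43 and 63 are antibody visits. Many early samples would therefore also follow a dose taken the day before. Protocol 8.5.3.4 allows the concentration sample at any time during the visit, so some gap is possible. These dosing-time passages do not fit together cleanly and need reconciling.

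The off-drug extreme is also limited. Values below quantification cannot be logged without a rule, and the SAP's half-LLOQ rule covers C-peptide only. If such subjects drop out of the regression, the distortion shrinks. Early tests with higher concentrations and early tests off drug push in opposite directions and may partly cancel.

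Finally, liraglutide's contribution is judged by the randomised comparisons, and nothing is decided on this coefficient. That stands and sets the weight of the point.

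**Conclusion.** The weakness is real but conditional. The planned regression can reject with no true concentration effect if C-peptide declines in the liraglutide arms and concentration differs between early and week-54 last tests. An MMTT done off drug at withdrawal is the most plausible route. On the pairings of preservation and SD that the SAP states, false rejection runs from nominal to about 17–19% (65%, SD 1) or about 12% (85%, SD 0.5), and it stays nominal at 98%. The upper ends need every early last test to be off drug, and the 21% share is itself an upper bound.

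A reader might infer that the test is invalid whatever happens, or quote false rejection of 20% to over 50%. The documents support neither. The test holds its level without a shift or without decline. The large figures combine the placebo preservation of 65% with the SD of 0.5 assumed for the combination, which the SAP never pairs, and add a large assumed shift. The issue is minor, but cheap to remove.

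**What to change.** In the two liraglutide arms, replace the LOCF basis with the primary MMRM. Add log concentration at each MMTT visit as a covariate with a visit-dependent coefficient, and report the week-54 coefficient. The SAP's biomarker analysis already uses this structure with baseline values, and liraglutide samples are scheduled at every on-treatment MMTT visit. Alternatively, use observed week-54 MMTTs only. At the least, add time of the last MMTT to the LOCF model.

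In each version, apply the SAP's own exclusion of MMTTs more than one day after the last liraglutide dose. It removes off-drug withdrawal tests and keeps week-54 tests done as scheduled. A broader rule dropping every test after liraglutide was stopped would, read literally, remove all the week-54 tests. State how a withdrawal-visit MMTT is assigned to a visit and how concentrations below quantification are handled.

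The cost is SAP wording and a modified model; no new data are needed. Slightly fewer observations remain. The week-54-only version uses about 152 × 240/304 = 120 subjects and conditions on completers. None of these versions makes concentration a randomised exposure, so the result stays descriptive.
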